# 6 PROPOSED RESEARCH OUTPUTS

Provision of early, high-quality acute care has been shown to improve clinical outcomes in specific diseases such as paediatric sepsis and head trauma.[16, 17] It is unclear how these findings apply to the vast majority of critically ill children who require stabilisation and transport to a PICU by PICRTs. We will examine whether and how timeliness of access to paediatric intensive care and care delivered during acute stabilisation and transport affect clinical outcomes and experiences of critically ill or injured children with a range of diagnoses and pre-existing medical conditions, so that findings can be generalised to all critically ill children.

Positive and negative experiences of families and clinicians will be used to inform the development of new clinical guidelines to ensure that they address the concerns and needs of patients, families and those who care for them. Whilst the stresses associated with PICU are well understood (for both families and clinicians),[13, 18] evidence about experiences associated with PIC retrieval is anecdotal at best. Understanding experiences will enable information, preparation and support to be tailored to the needs of families, with the potential to reduce levels of acute stress and anxiety and improve psychological outcomes in the longer term.

Centralisation of specialist acute care has occurred in several NHS services such as stroke, trauma, and specialist paediatrics.[4, 19] The findings from our research, particularly our novel approaches employing mathematical modelling, can provide evidence that can be generalised to evaluate other such centralisations. This is especially relevant to questions related to the trade-off between timeliness of access to acute care and provision of high quality cost effective specialist care.

# 7 STUDY DESIGN

DEPICT is a multi-disciplinary mixed-methods study comprising four linked work streams culminating in a series of workshops (See Appendix A for Study Flow Diagram):

A. Quantitative analysis of national paediatric intensive care audit data (PICANet) linked to routine administrative data (Hospital Episode Statistics in England and Patient Episode Database for Wales), death registrations (Office of National Statistics) and adult critical care data (Case Mix Programme).

[This analysis will be conducted retrospectively using data collected as part of national audit during a 3-year period between 2014 and 2016].

- B. Qualitative and questionnaire study involving interviews of parents of critically ill children transported to PICU (and children themselves, where feasible); interviews with clinicians working in PICUs, PICRTs and acute general hospitals and service managers/commissioners; and questionnaires to collect feedback from parents of transported children.
   [This workstream will involve prospective recruitment of patients over a 12-month period in 2017-18].
- C. Health economic evaluation of the costs and value for money of different models of PICRTs to identify cost-effective models of service delivery.
   [This workstream will involve analysis of costs and children's outcomes collected as part of the previous workstreams].
- D. **Mathematical modelling**, including the use of location-allocation optimisation, to explore the potential clinical and cost impact of alternative models of service and geographical locations where PICRTs could be based.

[This workstream will involve modelling using the findings of the previous workstreams].

E. **Workshops** involving key stakeholders: children and young people, parents, clinicians, and service managers/commissioners.

The study will involve the participation of all 10 PICRTs and 24 PICUs in England and Wales (representing 21 individual NHS Trusts).

## 8 RESEARCH PLAN

The study population will be critically ill children and young people (age <16 years) who are transported for emergency admission to a participating PICU in England and Wales.

#### 8.1 Workstream A: Quantitative analysis

The two main objectives of the quantitative analysis are:

Objective 1.1: To study the association between timeliness of access to paediatric intensive care and clinical outcomes, and

Objective 1.2: To study the association between care delivered by PICRTs and clinical outcomes.

#### 8.1.1 STUDY DATASET

We will generate a linked dataset for the study from several data sources:

1. National paediatric intensive care audit data from the Paediatric Intensive Care Audit Network (PICANet, www.picanet.org.uk).

PICANet is commissioned by the Healthcare Quality Improvement Partnership (HQIP) as part of the National Clinical Audit Programme and is based at the Universities of Leeds and Leicester. PICANet data contain detailed clinical information regarding the case mix (age, diagnosis and severity of illness), resource use (daily organ support interventions) and outcome (such as length of PICU stay and vital status at discharge) of critically ill children. Detailed data regarding the transport are also included in PICANet. Data quality is ensured using precise rules and definitions applied by trained local data collectors at each participating unit, and both local and central validation checks to ensure completeness, logic and consistency.

2. Hospital Episode Statistics (HES, http://content.digital.nhs.uk/hes)

Administrative data related to A&E attendances and inpatient admissions to NHS Trusts in England are routinely collected as part of the HES Admitted Patient Care (APC) and Accident & Emergency (A&E) datasets. HES data contain demographic information (age, gender, ethnicity), clinical information (diagnoses and procedures), geographical information (address, site of treatment) and administrative information (time waited in A&E, hospital length of stay). Automatic data cleaning rules are completed at various stages in the cleaning and processing cycle. Similar APC and A&E data for Wales can be accessed from the NHS Wales Informatics Service's Information Services Division as part of the Patient Episode Database for Wales (PEDW).

3. Death registrations, ONS (http://content.digital.nhs.uk/onsmortality)

The Office for National Statistics collects data regarding the date and cause of death, as well as location of death, as part of death registrations in England and Wales. These data can also be accessed through the HES-ONS linked mortality data set.

4. National adult intensive care audit data, CMP (www.icnarc.org/Our-Audit/Audits/Cmp/About) National audit data are submitted by all adult, general critical care units in England, Wales and Northern Ireland to the Case Mix Programme Database (CMP) at the Intensive Care National Audit and Research Centre (ICNARC). The CMP contains detailed clinical information regarding case mix (age, diagnosis), resource use (organ support interventions) and outcomes (length of stay, vital status at discharge, discharge destination) of critically ill adults and children admitted to adult ICUs.

#### 8.1.2 DATA LINKAGE

#### 8.1.2.1 Purpose of data linkage

While PICANet data contain detailed clinical information regarding the transport, patient case mix, resource use and short-term outcome of transported critically ill children, there is limited information in PICANet regarding the patient pathway immediately prior to transport (such as length of time spent at the referring hospital and wards where the patient was cared for, whether admitted to the adult ICU for stabilisation prior to transport, and interventions performed). Linking PICANet data to HES data (and similar data from NHS Wales) for the acute hospital admission prior to transport and to CMP data (if the patient is admitted to an adult ICU) will provide a clearer understanding of the level of care provided to the child before transport to PICU - these factors are likely to significantly confound the association between timeliness of access to paediatric intensive care and clinical outcome. Therefore, it is crucial that information regarding pre-transport care is available for this study, which we plan to obtain from PICANet data linkage to HES and CMP. Similarly, PICANet data are limited to the PICU stay, which means that longer term outcomes of the patient such as 30- and 90-day mortality as well as healthcare resource use following PICU discharge are not available from PICANet. Data linkage to HES/ONS is vital to ensure that data related to 30-day mortality (study primary outcome), as well as other longer term clinical outcomes (secondary outcomes), is available.

See Appendix B for an example patient pathway for a critically ill child requiring transport to PICU.

## 8.1.2.2 Study data and generating the linked dataset

We will extract relevant PICANet data related to the transport and the PICU admission episode from all transported admissions to participating PICUs in England and Wales with an admission date during a 3-year study period (1 Jan 2014 to 31 Dec 2016). To ensure a high-quality dataset, we will apply a series of data cleaning rules including individual data range checks and inter-variable validation to the study data set to identify and clean common and obvious data quality errors prior to analysis.

We will apply for HRA CAG approval for this study. See Appendix C for data flows during the linkage process.

Data linkage will be undertaken by the NHS Digital Data Access Request Service (DARS) acting as a 'trusted third party'. PICANet have experience of successfully linking PICANet data to HES/ONS data through HSCIC in the past. The availability of NHS numbers in a very high proportion of PICANet (98%) and CMP records for children (97%) provides reassurance that most records can be successfully matched using a minimal number of patient identifiers. PICANet data, including identifiers, is currently held at the University of Leeds. University of Leeds will upload a list of patient identifiers (NHS numbers, date of birth, name and postcode) and a unique DEPICT study number to secure servers at NHS Digital for a cohort of children admitted to PICUs in England

during a 3-year period (2014-16) – Dataset 1. Similarly, ICNARC will upload a similar list of patient identifiers and a unique local CMP identifier for children admitted to AICUs in England during the same 3-year period (2014-16) – Dataset 2. No clinical information will be transferred to NHS Digital. NHS Digital will first merge Dataset1 with Dataset 2. The merged dataset will then be linked to HES/ONS data. A pseudonymised dataset consisting of DEPICT study number, Unique CMP identifier, and HES/ONS data will be returned from NHS Digital to the University of Leicester. University of Leicester will send a list of DEPICT study numbers to University of Leeds and a list of unique CMP identifiers and corresponding DEPICT study numbers to ICNARC. University of Leeds will send PICANet clinical data for the DEPICT study numbers to the University of Leicester. Similarly, ICNARC will send CMP clinical data for the DEPICT study numbers to the University of Leicester. Similarly, ICNARC will send CMP clinical data for the DEPICT study numbers to the University of Leicester. Similarly, ICNARC will send CMP clinical data for the DEPICT study numbers to the University of Leicester. Similarly, ICNARC will send CMP clinical data for the DEPICT study numbers to the University of Leicester. Similarly, ICNARC will send CMP clinical data for the DEPICT study numbers to the University of Leicester.

Data linkage for A&E and Admitted Patient Care (APC) data for care received in Wales will be conducted by NHS Wales Informatics Service in a similar flow as for the English data. A list of eligible NHS numbers and a unique DEPICT or CMP study identifier will be passed from PICANet and ICNARC to NHS Wales. NHS Wales will identify which NHS numbers appear on both lists and this will be used to link each child with their hospital A&E data and data related to their clinical care. Matching will consider the fact that some children may be admitted to hospitals or PICUs on more than one occasion throughout the study period. This data will be passed to the University of Leicester in a pseudonymised form (i.e. the NHS number removed but the DEPICT and CMP study identifiers will remain). The University of Leeds and ICNARC will then pass clinical data to the University of Leicester using the DEPICT or CMP study identifiers to allow the data sources to be combined with the A&E and APC data from NHS Wales.

Matching will consider the fact that some children may be admitted to hospital (and PICU) on multiple occasions within the study period.

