## 4.2 Study rationale

#### 4.2.1 CLINICAL OUTCOMES FOR TRANSPORTED CRITICALLY ILL CHILDREN

Children cannot choose which hospital to go to when they are critically ill. It is therefore crucial that NHS acute services are organised and delivered in a way that ensures timely, equitable access to high quality care throughout the patient pathway. Each year, nearly 5000 children presenting to general hospitals with life-threatening illness or injury require to be transported by PICRTs to PICUs. Transported children represent one-third of all PICU admissions (and one-half of all emergency admissions). Yet, compared to the two other main patient groups (planned admissions and emergency admissions from within the same hospital where the PICU is located), they have the poorest clinical outcomes: their PICU mortality is nearly double that of planned PICU admissions (8% vs. 4%),[10] and they have a significant risk of long-term complications and considerable associated health and social care costs. It remains unclear whether this is solely because transported children are much sicker than other groups of critically ill children, or whether the timeliness of access to PICU expertise and the quality of care delivered by PICRTs prior to PICU admission may have an additional influence on clinical outcomes.

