#### 8.1.3.1 Clinical outcomes

Primary outcome: Mortality within 30 days following PICU admission (the first admission in case of multiple PICU admissions), established by data linkage with death registrations.

Secondary outcomes to include:

- a) Mortality at fixed time-points (PICU discharge, 90 days and 1 year following [first] PICU admission)
- b) Number of PICU admissions during study period and time to readmission (if applicable)
- c) Length of stay in PICU (number of days from PICU admission to discharge, for each PICU admission)
- d) Resource use in PICU (number of days of invasive ventilation, vasoactive agent therapy, renal replacement therapy and extra-corporeal life support during PICU stay, for each PICU admission)
- e) Length of hospital stay linked to the first PICU admission (number of days from hospital admission to hospital discharge)
- f) Number of A&E attendances in the 12 months following discharge from the first PICU admission
- g) Hospital resource use (total number of days admitted to hospital) in the 12 months following discharge from the first PICU admission.

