#### 8.3.2 MEASURING COSTS

There are three elements of the cost analysis: costs of PICRT transport; NHS/PSS costs in the shortand medium-run; and, NHS/PSS and societal costs in the long-run. A detailed cost analysis of transport by the PICRT will be carried out based on travel time, team composition, interventions performed and management of critical incidents. Unit costs for each of these items will be obtained from provider Trusts and 2014-2015 NHS Reference costs.

For NHS/PSS costs in the short- and medium-run, the main health care resource use categories following arrival at the PICU will include time spent in the PICU (also accounting for time on invasive ventilation, vasoactive agent therapy, renal replacement therapy and extra-corporeal life support), time spent on different wards in the hospital after discharge from the PICU, and the number of inpatient and day case admissions, A&E visits and outpatient visits up to one year. Unit costs for these items will be taken from 2014-2015 NHS Reference Costs. It will not be possible to measure costs outside the hospital during the first year (e.g., primary care costs) directly for each patient included in the analysis, but we will estimate these based on published estimates of primary care resource use associated with main diagnosis leading to PICU admission. These will be obtained from systematic literature searches. While there is considerable uncertainty in these costs, we expect them to be a small proportion of total costs when combined with hospital costs. Hence the uncertainty is unlikely to affect the results, though we will examine this in sensitivity analyses.

Long-run costs will be modelled from published sources based on systematic literature searches of the CEA Registry at Tufts University, the NHS Economic Evaluations Database, the Health Technology Assessment Database, the Research Papers in Economics Database and PubMed. These will include NHS/PSS and societal costs where possible. We will aim to identify published estimates of incremental discounted lifetime costs from NHS/PSS and societal perspectives associated with main diagnosis leading to PICU admission. Where these are not available directly we will compute annual incremental costs by age and model lifetime costs applying survival estimates and recommended discount rates.[23] Given the uncertainty in these estimates we will undertake extensive sensitivity analyses (see below).

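### As worded, the PICANet extract is limited to transported admissions and does not cover the PICU readmission outcome in Protocol 8.1.3.1(b)

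*Protocol*

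**What the plan says.** Protocol 8.1.2.2 opens with the extraction rule: "We will extract relevant PICANet data related to the transport and the PICU admission episode from all transported admissions to participating PICUs". The rule covers both England and Wales and is confined to admissions dated between 1 Jan 2014 and 31 Dec 2016. No other sentence says which PICANet episodes are taken. The sample size section (8.1.3.5) again describes the data as transported PICU admissions.

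The outcomes in 8.1.3.1 are worded more broadly. Outcome (b) is "Number of PICU admissions during study period and time to readmission (if applicable"). Outcomes (c), PICU length of stay, and (d), days of ventilation and other organ support, are both defined per PICU admission. None of the three is limited by route of admission. The economic evaluation (8.3.2) runs to one year, and there "the main health care resource use categories following arrival at the PICU will include time spent in the PICU", broken down by organ support.

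The linkage text later in 8.1.2.2 uses different terms. Dataset 1 carries identifiers and "a unique DEPICT study number to secure servers at NHS Digital for a cohort of children admitted to PICUs in England", without the word transported. Then "University of Leeds will send PICANet clinical data for the DEPICT study numbers to the University of Leicester". The section ends: "Matching will consider the fact that some children may be admitted to hospital (and PICU) on multiple occasions within the study period".

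**The concern.** Section 4.2.1 separates three routes into PICU: transport from another hospital, emergency admission from within the PICU's own hospital, and planned admission. A transported child who steps down to a ward of the PICU hospital and deteriorates there returns by the second route. A child brought back for a scheduled procedure returns by the third. Both are PICU readmissions in the ordinary sense of outcome (b), and neither is a transported admission.

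If the extraction sentence is applied as written, outcome (b) becomes a count of repeat transports and a time to re-transport, while still being reported as readmission. The same gap reaches later stays in (c) and (d), if those outcomes are meant to include readmissions, and the PICU component of one-year costs compared between retrieval team models.

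**Working it through.** The plan gives no figure to reproduce, so the check is mainly a comparison of passages.

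**1. Which later events does each rule cover?**

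| Event after the index transported admission | Counted by 8.1.3.1(b)? | In the extract under the opening sentence of 8.1.2.2? | Other source |
|---|---|---|---|
| Return by transport, by 31 Dec 2016 | Yes | Yes | HES/PEDW for the hospital admission |
| Return from a ward of the same hospital, by 31 Dec 2016 | Yes | No | HES/PEDW for the hospital stay |
| Planned PICU admission, by 31 Dec 2016 | Yes | No | HES/PEDW for the hospital admission |
| Any PICU return in 2017 within a year of a 2016 index admission | No, (b) is confined to the study period | No | HES/PEDW for the hospital admission; the PICU stay belongs in the one-year costs |

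The second and third rows are the mismatch for (b). The fourth concerns costs only.

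**2. Does the linkage text widen the extract?**
- Dataset 1 is described as children admitted to PICUs. Taken literally that is wider than the transported population in section 8 and in the opening sentence of 8.1.2.2, so the section describes two scopes.
- Clinical data are sent by DEPICT study number. The protocol does not say whether that number belongs to a child or to an admission, or which episodes go with it. If it is per child, all episodes could follow. This is not stated.
- The line on multiple admissions concerns matching. It fits repeat transported admissions as well as readmissions by any route.

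The linkage text therefore permits a wider extract without stating one.

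**3. Can HES/PEDW fill the gap?** Section 8.1.2.1 assigns healthcare use after PICU discharge to the HES/ONS linkage, and 8.3.2 costs inpatient and day case admissions to one year. The hospital admission around a PICU return should therefore be seen. Nothing says that HES or PEDW will supply PICU readmission dates, PICU days or organ-support days. Section 8.1.1 gives PICANet as the source of daily organ support.

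**4. Size.** Missed readmissions = R × q, where R is the number of PICU readmissions and q the share not transported. The documents give neither. With q assumed between 0.2 and 0.8:
- R = 500: 500 × 0.2 = 100 to 500 × 0.8 = 400
- R = 1,500: 300 to 1,200
- R = 3,000: 600 to 2,400

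These values show only how wide the uncertainty is. The nearest figure is in 4.2.1: "Transported children represent one-third of all PICU admissions (and one-half of all emergency admissions"). It gives 1 − 1/3 = 2/3 of all PICU admissions, and 1 − 1/2 = 1/2 of emergency admissions, as not transported. That is the route mix of all PICU patients, not of readmissions among transported children.

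**5. Date limit and one-year costs.** Assume index admissions are spread evenly over the three years, and ignore deaths. Then 1/3 fall in 2016, and on average 1/2 of their one-year window lies after 31 Dec 2016. If the date limit also applies to readmissions, 1/3 × 1/2 = 1/6 of one-year follow-up time has no PICANet cover.

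**The case against.** The best defence is that the opening sentence of 8.1.2.2 says who enters the cohort, and that the data flow then returns those children's PICANet records by study number, with repeat admissions foreseen. That is a fair reading and may be the intention. A reader might infer from the opening sentence that every non-transported readmission will certainly be lost. The documents do not support that: they conflict, and the wider reading remains open.

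Outcomes (c) and (d) can also be read as applying to transported admissions only, because time to bedside, team composition and transport incidents exist only for a transport. On that reading the extract covers them. This stands, so the point on (c) and (d) is conditional.

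A reader might also infer that one-year costs lose these readmissions altogether. They do not, since HES/PEDW should capture the hospital admissions. What would be missing is PICU-level days and organ support.

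Two further inferences go too far. One takes 1/2 to 2/3 as an estimate of the share missed; no readmission data lie behind it. The other holds that the loss is non-random, because the place of recovery may vary with distance or retrieval region. That is plausible, but no section says where transported children recover.

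Finally, (b) is one of seven secondary items, is not in the synopsis list, and detail could be left to the analysis plan. Its standing limits the weight of the point. But an analysis plan cannot recover episodes that were never extracted, so the scope has to be right in the data specification.

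**Conclusion.** The only stated extraction rule does not deliver outcome 8.1.3.1(b). Applied literally, (b) measures re-transport rather than readmission. Outcomes (c) and (d) are affected only if they are meant to include readmissions, and one-year costs only in their PICU-day and organ-support part. The linkage text suggests a wider scope without stating it, so the protocol is inconsistent; it is not certain to lose the data.

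The size of any loss cannot be computed from the documents. The ranges above rest on assumed readmission numbers, an assumed route share and an even spread of index admissions. Thirty-day mortality, the other mortality outcomes, and length of stay and organ support for the index stay are unaffected. The point should be corrected, but it does not threaten the primary analysis.

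**What to change.** In 8.1.2.2, define the cohort by the index transported admission. State that all later PICANet admissions of those children, from any source (transported, same-hospital emergency or planned), are extracted through the follow-up window. For one-year costs of 2016 index cases the window must run into 2017. Use these records for outcome (b), for (c) and (d) where readmissions are meant, and for PICU costs. Align the description of Dataset 1 with this, and say whether the DEPICT study number identifies a child or an admission.

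If the wider extract is not wanted, relabel (b) to (d) as restricted to transported admissions, and state the same limit for the PICU part of one-year costs.

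The cost is a wider PICANet query on children already in the cohort and a line in the data application. The records come from an existing audit, so no new collection is needed.

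### The written linkage makes no provision for death registrations of children admitted to PICUs in Wales, or for the outpatient visits used in the one-year costs

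*Protocol*

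**What the plan says.** **Deaths.** Protocol section 8.1.2.2 extracts PICANet records "from all transported admissions to participating PICUs in England and Wales with an admission date during a 3-year study period". Section 8.1.3.1 defines the primary outcome as 30-day mortality "established by data linkage with death registrations". Section 8.1.2.1 explains that PICANet stops at the end of the PICU stay and adds: "Data linkage to HES/ONS is vital to ensure that data related to 30-day mortality (study primary outcome".

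The route to those deaths is in section 8.1.2.2. PICANet identifiers go to "secure servers at NHS Digital for a cohort of children admitted to PICUs in England". They are merged with a second list of children admitted to adult ICUs, also limited to England, and then: "The merged dataset will then be linked to HES/ONS data". Section 9 repeats this route with the same restriction. For Wales, section 8.1.2.2 says: "Data linkage for A&E and Admitted Patient Care (APC) data for care received in Wales will be conducted by NHS Wales Informatics Service". The same paragraph ends by naming A&E and APC as the Welsh data to be combined with the audit records. It does not mention deaths.

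**Outpatients.** The main resource categories in section 8.3.2 include "A&E visits and outpatient visits up to one year". Section 8.1.1 describes the English administrative source as the "HES Admitted Patient Care (APC) and Accident & Emergency (A&E) datasets" and names the same two types of data for Wales. Section 8.3.2 concedes that costs arising outside the hospital, such as primary care, cannot be measured directly. It makes no such concession for outpatient visits.

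**The concern.** In both cases an analysis needs an input that no written step supplies.

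For deaths, the cohort covers two countries but the described ONS link covers admissions in one. Followed literally, the text would leave PICANet vital status at PICU discharge, and whatever hospital deaths the Welsh APC data happen to show, as the only mortality information for children admitted to a PICU in Wales. Neither is the outcome defined in section 8.1.3.1. The gap would apply to the primary outcome and to 90-day and one-year mortality. It would also undercut section 8.3.3, which says mortality to one year is measured directly in the study.

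For outpatients, section 8.3.4 promises a patient-level cost dataset for every patient, yet one of the listed hospital categories has no activity source.

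Neither input can be recovered at the analysis stage if it was never requested. The linkage text defines whose identifiers are sent and which datasets come back, so it is the place to settle both.

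**Working it through.** The plan states no figure on this point, so the check is a trace of each required input to a named source and a written route. Arithmetic is used only for size.

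**Step 1. Trace of inputs**

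| Input needed | Source named | Written route, PICUs in England | Written route, PICUs in Wales |
|---|---|---|---|
| Death in PICU | PICANet vital status (8.1.1) | PICANet | PICANet |
| Death after PICU discharge, to 30 days, 90 days and 1 year | ONS registrations, covering both countries (8.1.1) | NHS Digital HES/ONS link (8.1.2.2, 9) | None described in the text |
| Inpatient and A&E activity | HES APC and A&E; Welsh equivalents (8.1.1) | NHS Digital | NHS Wales Informatics Service |
| Outpatient activity to 1 year | None named | None described | None described |

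Children who live in Wales but are admitted to a PICU in England are on the English list. The gap concerns admissions to PICUs in Wales only.

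**Step 2. Size of the Welsh gap**

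Inputs: about 15,000 transports, 30-day mortality of about 7% and a minimum of 9,685 transports (all section 8.1.3.5); 24 PICUs (section 7). The Welsh share is not given. I assume 1% to 8%. One PICU of average volume would be 1/24 = 4.2%, inside that range.

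- Transports = 15,000 × share: 15,000 × 0.01 = 150; 15,000 × 0.08 = 1,200.
- Total 30-day deaths among them = transports × 0.07: 150 × 0.07 = 10.5; 1,200 × 0.07 = 84.
- At 1/24: 15,000/24 = 625 transports; 625 × 0.07 = 43.8 deaths.

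These are all 30-day deaths in the group. PICANet already records those that occur in PICU, so only deaths after PICU discharge could be missed. The protocol does not give the split, so the number at risk cannot be computed; it is at most these totals.

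**Step 3. Is the sample size threatened?**

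- Transports left if every Welsh PICU admission were excluded: 15,000 − 150 = 14,850; 15,000 − 1,200 = 13,800. Both exceed 9,685.
- Share needed to fall below the minimum: 1 − 9,685/15,000 = 35.4%.

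No plausible Welsh share approaches that. The issue is ascertainment and coverage, not power.

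**Step 4. Could outpatient activity come from elsewhere in the plan?**

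Section 8.3.1 says the workstream A sources will be supplemented with cost data. Section 8.3.2 describes those as unit costs from provider Trusts and NHS Reference Costs. They are prices, not counts of visits. The literature-based estimates in section 8.3.2 are reserved for care outside the hospital in the first year and for long-run costs. Outpatient visits fall into neither group.

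**The case against.** The strongest objection is that section 8.1.2.2 refers the reader to Appendix C, which has a separate heading for the Welsh flow, and that diagram is not visible. It may show a death link. The protocol also names ONS registrations as a source covering both countries, says the HES-ONS set is one way to reach them, and describes the Welsh linkage as similar to the English one. Section 9 contains no Welsh flow at all, so its England-only wording may simply not have been updated and is weak evidence of an intention to exclude Wales.

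Much of this stands. A reader might infer that the study cannot obtain Welsh deaths; the documents do not support that, because the source is named and only the written route is absent. What remains is that the comparison with the English flow is made for A&E and APC data, and no visible sentence submits Welsh PICU admissions for death linkage. If the diagram does include deaths, the prose in 8.1.2.2 and 9 still needs to match it.

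On size, a reader might take the 44 deaths at a 1/24 share as deaths lost. That is a total under an assumed share, and it includes deaths in PICU that PICANet already holds. Nor do the documents say which retrieval services bring children to PICUs in Wales, so the gap cannot be placed in one service.

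On outpatients, section 8.1.2.2 refers to HES data generically and the data-access applications are not visible, so a complete absence of outpatient data does not follow. The category is also one of several in a secondary economic analysis. The objection reduces the weight of this part, but the source remains unnamed.

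**Conclusion.** Both gaps hold as gaps in the written plan.

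1. The text provides no death-registration link for children admitted to PICUs in Wales. Unless Appendix C supplies one, their deaths after PICU discharge lack registry ascertainment at 30 days, 90 days and one year. Under an assumed 1–8% share this concerns 150–1,200 transports and about 10–84 total 30-day deaths, of which an unstated part falls after PICU discharge. Power is unaffected.
2. The text counts outpatient visits to one year as a measured hospital category but names no dataset that records them.

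A reader might go further and infer that unlinked Welsh children would be counted as survivors, that outpatient costs would be set to zero, or that the comparison of service models would be biased in a particular direction. The documents do not support these readings. Section 8.1.3.4 leaves missing values to the statistical analysis plan, which is not at hand, and nothing visible fixes how unlinked records or absent outpatient counts would be treated.

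The point still merits correction, because data that were not requested cannot be restored by any later analysis.

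**What to change.** **Deaths.** In sections 8.1.2.2 and 9, extend the list sent for ONS death linkage to PICU admissions in both England and Wales. Alternatively, add death registrations to the written Welsh flow. Either way, check the wording against the Welsh diagram in Appendix C so that text and figure agree, and add the Welsh flow to section 9.

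**Outpatients.** Add the HES outpatient dataset and its Welsh equivalent to section 8.1.1 and to the data applications. If they cannot be obtained, move outpatient visits in section 8.3.2 to the group estimated from published sources, alongside primary care, and include them in the sensitivity analyses.

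**Cost.** Protocol wording and an extra line in the data applications, with a modest addition to data charges or approval time. The literature-based option for outpatients avoids the data charge but gives up patient-level measurement of that category.
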